2.5.3 Handling of missing values/censoring/discontinuations

If a patient has no value at Week 8, the missing value will be imputed as non-responders.

Average NRS spinal pain score will be calculated only if total and nocturnal pain score are non-missing.

2.5.4 Sensitivity analyses

The average spinal pain and raw (total and nocturnal spinal pain separately) NRS scores will be analyzed using a repeated measures analysis of variance (ANOVA) model. The model will include the same factors as the logistic model of primary analysis plus the respective baseline score as a covariate. Analysis visit will be used as repeat factor.

2.6 Analysis of the key secondary objective

There is no key secondary objective.

2.7 Analysis of secondary efficacy objective(s)

The secondary objective is to assess the proportion of patients with a BASDAI score < 4 at Week 8 of secukinumab 150 mg compared to placebo. The secondary endpoint will be analyzed analogous to the primary endpoint. The secondary endpoint will be included in a confirmatory testing strategy, it will be tested hierarchically after the primary endpoint.

2.7.1 Secondary endpoints

The secondary efficacy endpoint is the proportion of patients with a response of BASDAI score < 4 in secukinumab 150 mg and placebo at Week 8.

The analysis of the secondary variable will be based on the FAS-TP1 patients.

2.7.2 Statistical hypothesis, model, and method of analysis

The statistical hypothesis for BASDAI score < 4 being tested is that the odds of response at Week 8 are equal in the secukinumab 150 mg treatment group versus placebo group.

Let p_j denote the proportion of responders at Week 8 for treatment group j , $j=0, 1$, where

- 0 corresponds to placebo
- corresponds to secukinumab

In statistical terms, the following hypothesis will be tested:

$H_0: (p_1 / (1-p_1)) / (p_0 / (1-p_0)) = 1$ versus $H_A: (p_1 / (1-p_1)) / (p_0 / (1-p_0)) \neq 1$

In other words,

H_A : The odds ratio of achieving a response at Week 8 for secukinumab vs. placebo is different from 1.

The secondary analyses will be conducted analogous to the primary analyses, i.e., via logistic regression model with treatment, country and the stratification factor of prior exposure to TNF inhibitors (naïve/ inadequate responders to TNF α inhibitors) as factor. The Odds ratio, 95% confidence interval (CI) and p-value will be presented comparing secukinumab 150 mg treatment group to placebo group at Week 8. Confirmatory evidence for the superiority of secukinumab with respect to the secondary endpoint will be claimed only if the 2-sided p-value from the logistic regression model for the factor “treatment” is < 0.05 and if the direction is correct, i.e. if the odds of response are larger under secukinumab and if the superiority of secukinumab with respect to the primary endpoint has already been demonstrated.

Summary statistics will also be reported for each treatment group and by visit. Graphical representation will also be performed.

2.7.3 Handling of missing values/censoring/discontinuations

If a patient has no value at Week 8, the missing value will be imputed as non-responders. BASDAI score will be calculated based on the average of the non-missing answers available.

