### **13.8 Appendix 8: Bath ankylosing spondylitis disease activity index**

The BASDAI consists of a 0 through 10 scale (0 being no problem and 10 being the worst problem, captured as a continuous numerical rating scale), which is used to answer 6 questions (pertaining to the 5 major symptoms of AS):

1. How would you describe the overall level of fatigue/tiredness you have experienced?
2. How would you describe the overall level of AS neck, back or hip pain you have had?
3. How would you describe the overall level of pain/swelling in joints other than neck, back, hips you have had?
4. How would you describe the overall level of discomfort you have had from any areas tender to touch or pressure?
5. How would you describe the overall level of morning stiffness you have had from the time you wake up?
6. How long does your morning stiffness last from the time you wake up?

To give each symptom equal weighting, the mean (average) of the 2 scores relating to morning stiffness (questions 5 and 6) is taken. The mean of questions 5 and 6 is added to the scores from questions 1-4. The resulting 0 to 50 score is divided by 5 to give a final 0 – 10 BASDAI score. Scores of 4 or greater suggest suboptimal control of disease, and patients with scores of 4 or greater are usually good candidates for either a change in their medical therapy or for enrollment in clinical trials evaluating new drug therapies directed at AS. BASDAI is a quick and simple index (taking between 30 seconds and 2 minutes to complete).

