2.13 Other Exploratory analyses

All the exploratory efficacy evaluation will be performed on FAS-TP1 and FAS-TP2 population based on the corresponding treatment periods. Refer to [Table 1.2-1](#) of Section 1 for the list of exploratory endpoints.

The following exploratory efficacy variables will be analyzed on the FAS-TP1 and FAS-TP2 population at (Baseline to Week 8) and (Week 8 to Week 24) respectively for all applicable analysis visits unless otherwise specified.

- Spinal pain score: Average NRS spinal pain score will be calculated only if total and nocturnal pain score are non-missing.
- BASDAI score: It will be calculated based on the average of the non-missing answers available.
- ASDAS CRP
- Patient reported outcomes: FACIT-Fatigue[©], PASS, ASAS health index

- The average and raw (total and nocturnal) spinal pain NRS scores will be analyzed using a repeated measures analysis of variance (ANOVA) model with treatment, country and the stratification factor of prior exposure to TNF inhibitors (naïve/ inadequate responders to TNF α inhibitors) as factors and respective baseline NRS score as covariate. The least squares means of the two treatment groups, least squares mean difference and 95% confidence interval for the difference in the two treatment groups will be presented along with the p-value based on the fitted linear model.
- Formula for ASDAS-CRP calculation: ASDAS (CRP) = 0.121 x total back pain + 0,110 x patient global + 0.073 x peripheral pain/swelling + 0.058 x duration of morning stiffness + 0.579 x LN (CRP+1)
The parameters, which are taken from patient reported outcomes, are expected to have values 0-10. CRP needs to be in the unit mg/L.

All endpoints relating to exploratory objectives will be summarized descriptively. Summary statistics will include relative and absolute frequencies for the categorical variables and the number of patients (n), minimum, mean, median and maximum for continuous variables will be separately provided for both period I and period II. Time courses of response rates and mean NRS-scores will be displayed graphically.

The following categorical exploratory endpoints will also be summarized categorically as absolute and relative frequencies (proportions, %). Any improvement or reduction is referred to as 'response' for all the below mentioned endpoints.

- Proportion of patients in each treatment group with response in spinal pain score < 4 at Week 1, 2, 3 and 4.

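### Read literally, the SAP's BASDAI scoring rule departs from the protocol's Appendix 8 formula and sets no minimum number of answers, on the only confirmatory secondary endpoint

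*SAP*

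**What the plan says.** Protocol Appendix 8 (Section 13.8) defines the score in three steps. First, "To give each symptom equal weighting, the mean (average) of the 2 scores relating to morning stiffness (questions 5 and 6) is taken". Then "The mean of questions 5 and 6 is added to the scores from questions 1-4". Finally, "The resulting 0 to 50 score is divided by 5 to give a final" score from 0 to 10. It has no rule for unanswered items.

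SAP Section 2.7.3, on missing values for the secondary endpoint, first imputes a missing Week 8 value as non-response. It then says that the "BASDAI score will be calculated based on the average of the non-missing answers available". SAP Section 2.13, which is not a missing-data section, says the same of the score: "It will be calculated based on the average of the non-missing answers available". The SAP neither restates nor cites Appendix 8, and it does not say whether Q5 and Q6 are combined first.

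On the endpoint's status, SAP Section 2.7 says: "The secondary endpoint will be included in a confirmatory testing strategy, it will be tested hierarchically after the primary endpoint". SAP Section 4 declares no change to the protocol-specified analyses.

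**The concern.** The two documents do not describe the same calculation. Appendix 8 averages five symptoms; the SAP sentence, as written, averages answers, of which there are six. Protocol Section 9 refers the reader to the SAP for all analysis details, so a programmer working from the SAP has only that sentence. Section 2.13 writes out the ASDAS-CRP formula in full but gives no BASDAI formula.

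The rule also has no floor. The other multi-item patient-reported scores in the SAP each have a completeness condition: both ratings for spinal pain (2.5.3), at least 11 answers for FACIT-Fatigue, and no more than 20% missing for the ASAS Health Index (both 2.11). BASDAI has none, so a nearly empty questionnaire yields a score and escapes the non-responder imputation.

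At stake is who counts as a responder on a confirmatory endpoint with a sharp threshold at 4. The same threshold governs entry: Protocol Section 4.1 requires a total BASDAI of at least 4 at Baseline. If entry were scored by Appendix 8 and Week 8 by the literal SAP rule, a patient whose answers had not changed could enter as active and be counted as a responder.

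**Working it through.** **Figures in the plan.** The plan gives no computed figure for BASDAI. Its only one, 332 patients (SAP Section 3), concerns the primary endpoint. It reproduces with a continuity-corrected two-proportion formula (23.5% versus 43.6%, 3:1, 90% power, two-sided 5%): 83 on placebo, 4 × 83 = 332. BASDAI does not enter it.

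**Inputs.** The Appendix 8 formula, the SAP sentence in 2.7.3 and 2.13, and the response threshold of less than 4 (SAP 2.7.1).

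**Complete questionnaires.** Let m be the mean of Q1 to Q4 and t the mean of Q5 and Q6.

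- Appendix 8: B = (4m + t)/5, so stiffness has weight 1/5 = 20%.
- Literal SAP rule: P = (4m + 2t)/6, so stiffness has weight 2/6 = 33%.
- Difference: P − B = (2/15)(t − m). This is 0.13 points per 1-point gap between t and m, zero when they are equal, and at most (2/15) × 10 = 1.33.

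| Q1 to Q6 | Appendix 8 | Literal SAP rule | Shift |
|---|---|---|---|
| 5,5,4,4,2,2 | (18 + 2)/5 = 4.00, non-responder | 22/6 = 3.67, responder | (2/15)(2 − 4.5) = −0.33 |
| 4,4,3,3,5,5 | (14 + 5)/5 = 3.80, responder | 24/6 = 4.00, non-responder | (2/15)(5 − 3.5) = +0.20 |

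**Incomplete questionnaires.**

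- If only Q3 is answered and equals 2, the average of the available answers is 2.0: a responder, not a missing value.
- If Q1 alone is missing, averaging the five remaining answers gives stiffness 2/5 = 40%. Averaging the four remaining Appendix 8 components gives 1/4 = 25%. The SAP does not say which applies.

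**How many patients change class.** The documents contain no item-level data, so this part rests on assumptions: rounded 0–10 items, item SD 2.3, inter-item correlation 0.3 to 0.7, Q5–Q6 correlation 0.7, mean of Q1 to Q4 from 4.0 to 4.7, and mean of the stiffness items from 3.5 to 5.0. Comparing B < 4 with P < 4 on complete questionnaires, 2.2% to 5.9% of patients change class. The overall response rate moves by −3.4 percentage points (39.1% to 35.7%, stiffness items higher than the rest) to +2.8 (40.7% to 43.5%, stiffness items lower).

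**Effect on the comparison.** A second simulation assumed patient SD 1.8, item SD 1.2 to 1.5, the same stiffness shift of −1 to +1 in both arms, and arm means of 4.0 versus 5.0 or 4.3 versus 5.3. Switching the scoring rule moved the odds ratio by no more than about 0.04 and the risk difference by less than 1 percentage point.

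**The case against.** The strongest reply is that the SAP never replaces the formula. The sentence in 2.7.3 stands under a missing-values heading and does not mention six answers. SAP Section 1 says that deviations from the protocol are documented, and Section 4 lists none. On this view it is a missing-item rule applied on top of Appendix 8. The copy in 2.13 follows a spinal-pain sentence that is itself carried over from the primary endpoint's missing-values section, so both may be transplanted missing-data rules.

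That reading is available, and for this reason a deliberate change of formula is not shown. It does not close the gap. Section 2.13 states the rule as how the score is calculated, with no missing-data heading. Even as a missing-item rule, it leaves open the weight of stiffness and the minimum number of answers.

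It is also fair to say that very incomplete questionnaires should be rare. Protocol Section 6.4 and Appendix 9 have staff check completeness and encourage missing answers, on an electronic device. Appendix 9 nevertheless accepts an incomplete questionnaire if the patient still cannot finish, so the case needs a rule.

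A reader might infer that the treatment comparison on BASDAI is biased. The documents do not support this: the scoring rule is the same in both blinded arms, and nothing in them indicates that stiffness would differ from the other items by arm.

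**Conclusion.** The SAP's scoring text is ambiguous and, read literally, inconsistent with Appendix 8. The weight of stiffness (2/6 against 1/5), the shift of (2/15)(t − m) and the one-item responder follow from the wording alone. The 2% to 6% reclassified depends on assumed item distributions and on the literal rule being programmed; only patients near 4 whose stiffness answers differ from their other answers are affected.

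Two stronger conclusions are tempting. One is that patients will be misclassified: that holds only under the literal reading, which the SAP does not force. The other is that eligibility and response are judged on different scores: that further requires Appendix 8 to have been used at entry, and Protocol Section 4.1 names no second formula. No bias, loss of power or inflation of type I error is shown. The point should still be corrected before unblinding, because a confirmatory endpoint needs one unambiguous derivation consistent with the protocol.

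**What to change.** In SAP Sections 2.7.3 and 2.13, replace the averaging sentence with the following:

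- BASDAI = (Q1 + Q2 + Q3 + Q4 + mean(Q5, Q6))/5, citing Protocol Appendix 8.
- If only one of Q5 and Q6 is answered, that answer is the stiffness component.
- If exactly one of the five components is missing, the score is the mean of the other four.
- If more than one component is missing, the score is missing and the patient is a non-responder at Week 8.

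The completeness cut-off is the sponsor's choice, since the protocol gives none, but it must be fixed in advance. Should the average of all six answers really be intended, it belongs in SAP Section 4 as a declared change, with reasons.

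The cost is a few lines of text and one derivation. The downside is that a few partly answered questionnaires become non-response. The sample size is unaffected.

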2.8 Safety analyses

All the safety analysis will be performed on the Safety Sets for period I and period II separately and also for entire treatment period, where applicable. Summaries will be performed separately for period I (from baseline to Week 8) and period II (from dosing at Week 8 to Week 24).

The safety follow-up will be carried forward until 12 weeks after the last study treatment. The analyses of the follow-up period will be consolidated to summaries for treatment-emergent adverse events, and serious adverse events to Treatment Period 2.

Safety analyses will be performed on treatment received or actual treatment as described below:

The actual treatment or treatment received for summaries of safety data will differ to the treatment assigned at randomization only, if a subject received the wrong treatment during the entire study.

For those patients who received erroneously at least once, the wrong treatment (not the correct one at randomization) an additional AE listing will be prepared displaying which events occurred after the treatment errors and the relationship with study drug.

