1.1 Study design

This is a 24-week, randomized, double-blind, placebo-controlled, multicenter study to evaluate the efficacy and safety of secukinumab in controlling spinal pain in patients with axSpA. The study will consist of 2 treatment periods: a double-blind, placebo-controlled period from Baseline to Week 8 (i.e. Treatment Period 1) and a double-blind secukinumab treatment period from Week 8 to Week 24 (i.e. Treatment Period 2). At Baseline, patients will be randomized to either secukinumab 150 mg or placebo. At Week 8, patients will be re-randomized and re-assigned respectively to 1 of 5 treatment arms to receive either secukinumab 150 mg or secukinumab 300 mg.

The schematic of study design is given in Figure 1.1 below.

Planned number of patients and randomization

It is intended that a total of 352 patients (264 in secukinumab 150 mg group and 88 in the placebo group) will be recruited to compensate dropouts and protocol violators.

Patient eligibility criteria will be assessed during the Screening Period, which will occur for up to 10 weeks prior to randomization.

Treatment Period 1

At Baseline, patients whose eligibility is confirmed will be randomized to receive double-blind treatment with either secukinumab 150 mg or placebo (3:1) in Treatment Period 1 (Baseline to time of study drug administration at Week 8):

- **Group A:** secukinumab 150 mg (1 x 1.0 mL) s.c. administered at Baseline, Week 1, 2, 3 and 4
- **Group B:** placebo (1 x 1.0 mL) s.c. administered at Baseline, Week 1, 2, 3 and 4

Secukinumab 150 mg and matching placebo will be provided as 1.0 mL pre-filled syringes (PFSs).

On each treatment day during Treatment Period 1, one s.c. injection with either secukinumab 150 mg or placebo will be administered via PFSs.

Treatment Period 2

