2.2 Analysis sets

The following analysis sets will be used in this study:

The **Enrolled Set** will include all patients, who provided informed consent.

The **Randomized Set** will consist of all patients, who were randomized into this study at Baseline. Mis-randomized patients will not be included in this analysis set.

[figure not shown]
The **Safety Set for Treatment Period 1 (SAF-TP1)** will consist of all patients, who received at least 1 dose of study treatment during this treatment period. Data will be analyzed according to the treatment actually received.

The **Safety Set for Treatment Period 2 (SAF-TP2)** will consist of all patients, who received at least 1 dose of study treatment during this treatment period. Data will be analyzed according to the treatment actually received.

The **Safety set (SAF)** will consist of all patients, who received at least one dose of study treatment. To analyze entire study period safety assessments, this dataset will be used.

The **Full Analysis Set for Treatment Period 1 (FAS-TP1)** will consist of all patients, who were randomized into this study at Baseline and received at least 1 dose of study treatment during this treatment period. Data will be analyzed according to the treatment assigned at randomization.

The **Full Analysis Set for Treatment Period 2 (FAS-TP2)** will consist of all patients, who were re-randomized or re-assigned at Visit 7 (Week 8) and received at least 1 dose of study treatment during this treatment period. Data will be analyzed according to the treatment assigned at randomization.

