2.4 Treatments (study treatment, rescue medication, concomitant therapies, compliance)

2.4.1 Study treatment / compliance

Study Treatment

The summaries by treatment will be performed by the actual treatment received (as follows) for each treatment period.

Treatment group for period I:

- Group A: AIN457 150 mg
- Group B: Placebo

Treatment group for period II:

- Arm A1: AIN457 150 mg
- Arm A2: AIN457 150 mg
- Arm A3: AIN457 300 mg
- Arm B1: AIN457 150 mg
- Arm B2: AIN457 300 mg

The analysis of study treatment data will be based on the safety set for period I, period II and the entire treatment period separately. The number of active and placebo injections will be summarized by treatment group up to Week 8, the number of double blind injections will be summarized by treatment group from Week 8 to Week 24.

Rescue medication

Not applicable.

Duration of exposure

The duration of exposure to study treatment will be summarized by treatment group. In addition, the number and percentage of patients with cumulative exposure levels (e.g. any exposure, ≥ 1 week, ≥ 2 weeks, ≥ 3 weeks, ≥ 4 weeks, ≥ 8 weeks, etc.) will be presented.

Duration of exposure for secukinumab groups will be defined as the time from first dose of study treatment to the time of treatment end for each treatment period. Duration of exposure for the placebo group will be defined as the time from first dose of placebo treatment to the time of treatment end in treatment period 1 and the time from first dose of active treatment to the time of treatment end in treatment period 2.

For patients who discontinue, this will be the patient's last visit in the corresponding treatment period.

Duration of exposure (years) = duration of exposure (days) / 365.25

Duration of exposure (100 subject years) = duration of exposure (years) / 100

The analyses of duration of exposure described above will be done for both the study treatment periods.

Compliance

Compliance will be calculated based on documented study drug administrations and syringe counts and displayed by treatment group.

Compliance is expected to be 100%, unless temporary interruption is needed for safety reasons. Compliance will also be assessed by a Novartis monitor using information provided by the authorized site personnel.

Compliance (%) = 100(total no of injections administered)/(no. of injections prescribed).*

Compliance for entire treatment period will be based on active treatment exposure.

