EXCL23	Patients with any medical or psychiatric condition, which would preclude the participant from adhering to the study protocol.	INCLUDE IN EVERYTHING	0
EXCL24	Patients with history or evidence of ongoing alcohol or drug abuse within the last 6 months before randomization	INCLUDE IN EVERYTHING	0
EXCL25	Patients with administration of live vaccines 6 weeks prior to randomization or plans for administration of live vaccines during the study period	INCLUDE IN EVERYTHING	0
OTH01	Pregnancy test not performed as required per protocol	INCLUDE IN EVERYTHING	0
OTH02	Spinal pain NRS score at week 8 is missing.	INCLUDE IN EVERYTHING	0
OTH03	Spinal pain NRS score at baseline is missing	INCLUDE IN EVERYTHING	0

Deviation ID	Description of Deviation	Exclusion in Analyses	Severity code
OTH04	Patient PRO data was not collected according to the protocol	INCLUDE IN EVERYTHING	0
WITH01	Pregnant patient not withdrawn from study	INCLUDE IN EVERYTHING	0
WITH02	ICF withdrawn but patient continuing in the study	INCLUDE IN EVERYTHING	0
TRT01	Dosing error in comparative dosing phase (too many injections in treatment phase 1 and 2)	INCLUDE IN EVERYTHING	0
TRT02	Dosing error in comparative dosing phase (less than 2 injections in treatment phase 2)	INCLUDE IN EVERYTHING	0
TRT03	No study medication administered.	INCLUDE IN EVERYTHING	0
TRT04	Patient randomized mistakenly in the study and did not receive study drug.	EXCLUDE FROM FAS and SAF	3
TRT05	The patient was re-randomized to the wrong treatment arm.	INCLUDE IN EVERYTHING	0
TRT06	Patient was randomized to the wrong stratum at baseline.	INCLUDE IN EVERYTHING	0
TRT07	Study medication was administered, which could have been damaged.	INCLUDE IN EVERYTHING	0
COMD01	Prohibited medication consumed during study.	INCLUDE IN EVERYTHING	0
COMD02	Painkillers intake during 24h before a visit involving a disease activity assessment.	INCLUDE IN EVERYTHING	0

Table 2 Analysis set exclusions based on population codes

Analysis set	Population codes that cause a subject to be excluded
RAN	NA
SAF	2, 3
FAS	1, 3

Table 3 Population code text

Population Code	Population code text
0	INCLUDE IN EVERYTHING
1	EXCLUDE FROM FULL ANALYSIS SET (FAS)
2	EXCLUDE FROM SAFETY SET (SAF)

3

EXCLUDE FROM FAS AND SAF

6 Reference

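### SAP 2.8 regroups a patient only if treatment was wrong throughout the study, so an error lasting one whole period stays under the assigned group in that period's safety tables

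*SAP*

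**What the plan says.** The safety sets are defined by period. SAP 2.2 describes SAF-TP1 and SAF-TP2 in the same terms, as the patients who "received at least 1 dose of study treatment during this treatment period. Data will be analyzed according to the treatment actually received". Protocol 9.1 gives the same definitions and attaches no further condition. SAP 2.2 also has a whole-study safety set (SAF), for which it names no treatment basis.

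SAP 2.4.1 treats exposure the same way: "The summaries by treatment will be performed by the actual treatment received (as follows) for each treatment period".

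SAP 2.8 keeps the split by period: "All the safety analysis will be performed on the Safety Sets for period I and period II separately", with whole-study summaries where applicable. It then defines the treatment to be used in summaries of safety data, which departs from the randomised treatment "only, if a subject received the wrong treatment during the entire study". For anyone given a wrong treatment on one or more occasions, "an additional AE listing will be prepared displaying which events occurred after the treatment errors and the relationship with study drug".

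There are two points of assignment. After the Baseline randomisation, SAP 1.1 states: "At Week 8, patients will be re-randomized and re-assigned respectively to 1 of 5 treatment arms". SAP section 4 records no change from the protocol's analyses.

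**The concern.** An as-treated table and an as-assigned table differ only in where the wrongly treated patients sit. The rule that decides when such a patient moves is therefore the working part of any as-treated definition. Here the sets and the tables are by period, but the rule looks at the whole study. A patient whose every dose in one period was wrong can be kept in the assigned column for that period because the other period was right.

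At stake is where adverse events are counted. In Period 1, events under secukinumab could be counted as placebo events. In Period 2, events under one dose level could be counted under the other. The same sentence governs the crude AE and SAE tables, the death summaries and the exposure-adjusted rates (SAP 2.8.1 and 2.8.2). If SAP 2.4.1 is programmed as written, exposure tables and AE tables could also show the same patient in different groups.

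**Working it through.** The plan gives no figure on this point, so there is none to reproduce. The check sets the rules side by side and then sizes one affected patient.

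**1. What the rule requires.** Period 1 has 5 dosing days (Baseline, Weeks 1, 2, 3, 4) and Period 2 has 4 (Weeks 8, 12, 16, 20), from SAP 1.1. For a patient who completes, 5 + 4 = 9 dosing days under two separate assignments would all have to be wrong.

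**2. Cases under the two rules.**

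| Patient | Set | By treatment received in the period (SAP 2.2) | By the whole-study condition (SAP 2.8) |
|---|---|---|---|
| Group B, given secukinumab at all 5 Period 1 doses, correct from Week 8 | SAF-TP1 | Secukinumab | Placebo |
| Correct in Period 1, assigned to A2, given 300 mg at all 4 Period 2 doses | SAF-TP2 | 300 mg | 150 mg |
| Wrong at all 9 dosing days | Both | As received | As received |
| Stops in Period 1 after only wrong drug | SAF-TP1 | As received | As received, on a natural reading |
| Wrong at some doses within a period | Either | Not specified | As assigned, plus listing |
| Always correct | Both | No difference | No difference |

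The two rules conflict in the first two rows.

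**3. Whole-study tables.** SAP 2.8.1 leaves placebo time out of the exposure-adjusted rates for the entire treatment period. For the patient in the first row, it is therefore unclear whether the 8 weeks of Period 1 count as active exposure, because SAP 2.2 gives no treatment basis for SAF.

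**4. Weight of one patient.** Planned numbers are 264 and 88, and the assumed secukinumab response is 43.6% (SAP section 3).
- Group B: 1/88 = 1.1%.
- A2 or A3: 264 × (1 − 0.436) = 148.9 non-responders; 148.9/2 = 74.4; 1/74 = 1.4%.
- B1 or B2: 88/2 = 44; 1/44 = 2.3%.

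The last two assume 1:1 re-randomisation, which the documents do not state.

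**5. How often the rule could act (illustration only).** The documents give no error rate. Suppose the chance of wrong drug for a whole period is e, independent between periods, and all patients complete. The share of patients with a whole-period error whom SAP 2.8 would regroup is e² / (1 − (1 − e)²). This is 0.25% at e = 0.5%, 0.5% at 1%, 1.0% at 2% and 2.6% at 5%. If instead errors struck single doses independently at 1%, the expected number wrong at all four Period 2 doses would be 352 × 0.01⁴, about 0.000004. Whole-period errors would then arise only from a cause that persists across doses.

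**The case against.** **The wording may just be loose.** SAP 2.8 does not say that it displaces SAP 2.2, and the whole-study condition would suit the SAF, which has no stated treatment basis. That is a plausible account of how the sentence arose. It does not settle the matter, because the sentence is written for safety summaries in general and stands in a section that requires them by period. A programmer would apply it as written.

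**The listing is a real safeguard.** It covers anyone with at least one wrong dose, so it includes both conflicting cases above and the events would be visible. It does not move them in any table or rate.

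**The cases are remote.** Medication numbers come from the IRT (Protocol 5.3 and 5.5.2) and clinic injections are supervised (Protocol 5.5.4). No deviation code in SAP 5.5 describes wrong drug for a whole period. This stands, and it limits the size of the point.

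**Any threshold is a convention.** A rule based on every dose in a period still leaves a patient with four of five wrong doses in the assigned group. This also stands; the listing is the means of handling such patients.

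Two stronger readings are tempting, and the documents support neither:
- A reader might infer that the safety sets are not analysed as treated at all, or that the rule can never act. For correctly dosed patients assigned and received treatment coincide, and the rule can still regroup someone who stops in Period 1 after only wrong drug.
- A reader might take deviation TRT05 in SAP 5.5, "The patient was re-randomized to the wrong treatment arm", as showing that the plan expects this problem. That is an assignment error. Such a patient normally receives the drug of the arm given by the IRT, so assigned and received treatment agree and the rule in 2.8 is not engaged. SAP 2.13 deals separately with incorrect responder status.

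**Conclusion.** The point holds in a narrow form. The whole-study condition in SAP 2.8 contradicts the per-period definitions in SAP 2.2 and Protocol 9.1, and it does not fit the per-period exposure summaries in SAP 2.4.1. The conflict concerns patients given the wrong drug at every dose of one period and correctly treated in the other.

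The number of such patients is unknown and probably very small. The percentages above are the weight of one hypothetical patient, not an expected bias. In groups of 44 to 88, one misplaced serious event would be noticeable, but the plan specifies no between-group safety test. The efficacy analyses, which follow assigned treatment, and the sample size do not depend on this rule. This is a low-priority correction of a stated rule.

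**What to change.** In SAP 2.8, replace the whole-study condition with this one: actual treatment differs from assigned treatment if the wrong treatment was received at every administration in the treatment period being summarised. Apply it separately to SAF-TP1 and SAF-TP2.

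Add one sentence giving the rule for the whole-study SAF, including how active exposure time is counted for a patient whose Period 1 treatment was wrong. Keep the additional AE listing for errors that affect only part of a period. State that SAP 2.4.1 uses the same definition, so that exposure and AE tables agree.

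The cost is one phrase and two short sentences in the SAP. No new data or analysis is needed, and no protocol change, since this brings SAP 2.8 into line with Protocol 9.1. It is best done before unblinding.
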